#### **5.4 Blood draws**

During the screening visit, all participants will have a blood draw to test for CRP levels to stratify the participants accordingly in High CRP and Low CRP groups. Participants will also have a blood sample drawn at the end of the screening visit to test immediately for Hepatitis B and C, HIV, autoimmune diseases (double-stranded DNA test), and rheumatoid factor; as well as to use in later analyses of inflammatory markers. Participants will have a blood sample drawn (approximately 16.5mL) at the screening visit, approximately 40 mL at the baseline visit, approximately 40 mL at the end of the study, 40 mL at the end of the open label phase. Blood samples will be used for doing tests for inflammatory markers and for measuring levels of Interleukin-6, Interleukin-10, TNF-alpha, and C-reactive protein. We will look at immunological markers by two methods; luminex and flow cytometry. The Luminex assay measures soluble proteins in the sera. Molecules such as IL-6 and TNF-alpha, MIP1-alpha, IFN-alpha, CRP will be assessed. We will include or alter molecules in the luminex assay based on the most recent literature as we near the end of sample collection. Flow cytometry will also be utilized. Flow cytometry will be used to measure the status of T cells which are important in suppressing such conditions as infectious disease and cancer. We will develop a series of markers that define the memory and naive phenotype of T cells along with their activation status and functionality. We will also assess additional cell subsets such as NK and macrophages. Molecules that will be assessed include but are not limited to; CD3, CD4, CD8, CD45RO, CD27, CCR7, CD69, CD33, CD68, CD56, CD16, CD38 and HLADR and CD11c -monocytes. Some blood will be retained and banked for future research. Additional blood is being collected for ex vivo isolation of human peripheral blood mononuclear cells (PMBC), which is another assessment of inflammation levels. This additional blood draw will be optional and offered to all depressed participants.

Participants will give blood for a liver-function test and for hematocrit levels to test for GI bleeding. Participants may also have 24-hour ambulatory blood-pressure monitoring. Participants may wear a cuff for 24 hours that is set to automatically take blood pressure every 15 minutes during the day and every 30 minutes during the night.

#### **5.5 Gastrointestinal Safety**

At the beginning of the study, GI/bleeding risks will be examined. Hematocrit levels will be tested in blood samples to assess this risk at baseline, and at week 2.

#### **5.6 Protocol Non-Conform Drugs**

Urine may be used to assess intake of protocol non-conform drugs by means of the Rapid Detect 10 Panel Test Dip Card, Rapid Detect, Inc., [name] (or similar). The drug screen includes for example Amphetamines (AMP), cocaine (COC), Tetrahydrocannabinol (THC), methamphetamine (mAMP), opiates (OPI), Phencyclidine (PCP), benzodiazepines (BZO), tricyclic antidepressants (TCA), barbiturates (BAR), and methadone (MTD). This can be done both prospectively and retrospectively.

CONFIDENTIAL

### 5.7 Ambulatory Blood Pressure Monitoring (ABPM)

Ambulatory blood pressure monitors (ABPM) are readily available to the investigators to assess ABP in this study protocol. The 90207 ABP monitors are compact and lightweight to optimize subject comfort and a choice of four cuff sizes further aids comfort while also maximizing accuracy.

ABPM will be guided by the AHA Scientific Statement, Council on High Blood Pressure (4). Recommendations relevant to the present study are:

- Select ABP cuff size according to Table 1,
- Select the non-dominant upper arm for ABPM measurements,
- Instruct the patient to hold the arm still by their side while the device is taking a reading.

**Table 1 Cuff Sizes for ABPM**

Cuff Size*	Arm circumference [cm]	Arm circumference [inches]
Small Adult	17-26	7-10
Adult	24-32	9-13
Large Adult	32-42	13-17
Extra Large Adult	38-50	15-20

\* The bladder of the cuff should encircle at least 80% of the arm circumference (4).

The monitors for the 24-hr ambulatory blood pressure measurements will be preset to assess BP every 20 minutes in the daytime, defined as 0600h to 2200h, and every 30 minutes during the nighttime, defined as 2200h-0600h (Error! Reference source not found.). Preset ranges for acceptable BP measurements are 60–250 mmHg systolic, 30-200 mmHg diastolic, 40-230 mmHg for mean arterial values, and 200 b/min for heart rate. ABP readings should cover  $\geq 80\%$  of the expected readings with interruptions of less than 1 hour. Awake and asleep times will be determined by patient diaries. This protocol is well established (5, 6).

Blood pressure cuff is usually mounted on the non-dominant arm of the patient connected through a hose with the recorder, which initializes the blood pressure measurements following the preset paradigm.

Experience in the field, however, informed us that the 24-hr ambulatory blood pressure measurements are tolerated by the patients only in varying degrees. Therefore, we will adapt the ABP settings to achieve tolerability. The minimum frequency of 2 measurements per hour during

CONFIDENTIAL

This material is the property of the University of Pennsylvania.

the day and 1 measurement per hour during the night will be observed as well as a minimum time of observation of 15 hours (e.g. 16:00 until 07:00 the following day).

### **5.8 Activity Diary**

Patients will be asked to fill out an activity diary during each of the 24 hour ABPM session. An example of the diary form is provided in the appendix.

### **5.9 Actigraphy**

Actigraphy will noninvasively assess and log the sleep, wake and activity patterns for each patient. In detail, data capture entails 24 hour sleep/wake measurements including total sleep time (TST), sleep latency, wake after sleep onset (WASO), sleep efficiency, energy expenditure, metabolic rates, steps taken, physical activity intensity, subject position, and ambient light levels.

This device will be applied as a wrist watch which facilitates incorporation into the clinical study setting. Actigraphy devices will be sources from e.g. ActiGraph, Pensacola, FL, <http://www.actigraphcorp.com/company/> or similar suppliers.

Participants will be asked to wear this device for the course of the study 6 weeks in total.

### **5.10 Drug concentrations in plasma**

Escitalopram and Celecoxib drug concentration will be determined in plasma and CSF (optional) using standard mass spectrometric methods.

### **5.11 Urinary Prostaglandin Metabolites**

If urine samples are available, drug effects of celecoxib are easily quantified by measuring prostaglandin metabolites in the spot urine collections. Spot urine collections will be stored at -80°C until analysis. The urinary prostacyclin metabolite, 2,3-dinor-6-keto-PGF1α (**PGI-M**), the thromboxane metabolite, 11-dehydro-thromboxane B2 (**TxB-M**), possibly also including 2,3-dinor-TxB-M and the prostaglandin metabolites 7α-hydroxy-5,11-diketotetranorprostane-1,16-dioic acid (**PGE-M**) and 11β-dihydroxy-15-oxo-2,3,18,19-tetranorprost-5-ene-1,20-dioic acid (**PGD-M**) will be quantified by LC/MS/MS. These assays are routinely performed in the Institute for Translational Medicine and Therapeutics' mass spectrometry laboratories with inter- and intra-assay variabilities of 4-8%.

### **5.12 Microbiome Analyses**

Microbiome can be analyzed through an optional stool sample or optional mouth swab (inside of both cheeks) and saliva collection. DNA from will be extracted from each sample; PCR amplified using 16S primers, and subjected to 454/Roche pyrosequencing. At least 1000 sequence reads will be used to characterize each community. The 16S sequence reads are then aligned using the NAST and GreenGenes servers and inserted into a well characterized phylogenetic trees of 16S sequences, allowing phylogenetic placement of each sequence read. As a first step in analyzing the global effects of each treatment, we will compare microbial communities using UniFrac, which quantifies the similarities among microbial communities

CONFIDENTIAL

based on phylogenetic distances. To compare two communities, sequences from both communities are placed on a common phylogenetic tree generated using ARB. The fraction of the branch length on the tree unique to each community is then measured. This provides a objective measure of community similarity based on the amount of shared evolutionary history. To compare multiple communities, distances between all pairs of communities are computed to generate a distance matrix and Principal Coordinate Analysis is used to plot communities in a scatter plot along orthogonal axes of maximal variance. Such scatter plots can be generated taking into account the abundance as well as the presence of each taxa (weighted UniFrac), or using only presence/absence information (unweighted UniFrac). The two methods thus address different questions--weighted analysis allows differences in proportional representation of community members to be assessed, while unweighted analysis discloses changes in community composition. Measures of alpha diversity such as the Chao1 and Shannon Indices will also be used to characterize communities. Saliva swab samples will be obtained for future unplanned analysis including DNA analyses specifically looking at the APOE genotype as it may affect treatment response.

### **5.13 Distribution and shipment of human specimens**

The human specimens collected for this study will be de-identified and will not contain any Protected Health Information (PHI) prior to in-house sample distribution or shipment to external collaborators.

## **6 Analysis Plan**

### **6.1 Data Analysis and Predictions**

At a basic level, the design of this trial is simple repeated measures design with a) two replicates (time points) b) baseline covariates and outcomes, and c) a single between-person factor (initial case-control depression status). The data collected at two time points to be included in analysis (pre- and post-treatment) will be the depression severity, inflammatory markers, resting state functional connectivity and neuropsychometric data. There have been no published studies to date examining adjuvant celecoxib and SSRI treatment in patients who simultaneously received assessment of inflammatory biomarkers. However, based on our own small pilot sample we will have greater than 85% power to detect differences in changes in IL-6 between SSRI responders and SSRI + celecoxib responders. Volumetric data and confounders to be included in the analysis will be collected at baseline. Classic models of change scores can be used where the baseline level can be controlled giving the so-called residual change score. Use of residualized change scores has several analytic advantages: (1) control for variance (the best predictor of today's value is yesterday's value), (2) statistically each subject is started at the same point. Thus, our estimation model will be extended from the classic model of change scores to a repeated measures ANOVA (analysis of variance) or mixed model repeated measures design. A joint modeling approach with mixed models for repeated measures data can be used to address within-subject variation and between-subject variation of the repeated measurements of multiple

CONFIDENTIAL

variables such as neuropsychological measures and inflammatory markers. Generalized linear models (GLM) will be used for the baseline data. We are aware that numerous other confounders exist (such as age, race, education, statin use and gender). When a variable is identified to be related to the outcome and covariate of interest, i.e. confounder, we will adjust for it in the model of choice. A sensitivity analysis of statin and/or ARB use will be performed via analysis by statin and ARB use to determine if it is necessary to adjust or stratify by statin and ARB use. Models consider inclusion of the list of known covariates and their interaction. The importance of these models will be assessed through inspection of the change in the parameter of interest, as well as the parameter (and p-value) for the covariate. Point estimates, p-values, and confidence intervals to test the covariate of interest will be computed. Mixed model diagnostics and GLM diagnostics will be evaluated. For the continuous outcomes, we will assess if transformations exist that can bring about near normality. In addition, the impact of skew on the stability of estimates can be assessed using bootstrap methodology. For all models involving skewed predictors, we will assess the impact of the significant outliers using bootstrap and will check the linearity assumption. Other diagnostic procedures will be used to check for the validity of the GLM assumptions such as normality of the residuals and linearity assumption. Missing data problems are ubiquitous in aging research. Missing values can arise from several sources, (1) subjects are lost to follow-up, (2) missing CRFs, or (3) particular items of a CRF are skipped. We will employ multiple imputation. In this design, we have numerous indicators of outcome and predictors. The concern is that the possibility of a Type-I error is increased if a series of univariate tests is employed. Several solutions are possible in the context of this design: 1) use of Bonferroni Corrections or the less conservative extension to Bonferroni corrections 2) use of data reduction techniques like Principal Component Analysis (PCA) , and 3) use of multivariate mixed models. Based on the estimated numbers of remitters vs non-remitters we expect to enter approximately 53 subjects in Phase II. Using the estimates from Abbasi et al. (7) for serum IL-6 comparing SSRI+celecoxib to SSRI+placebo, we will have greater than 95% power by randomizing the 53 subjects between the two groups.

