Hypothesis 1b: Cytokine levels will be correlated with hippocampal and amygdala volumes and PFC thickness; To examine correlational hypothesis 1b, we used a Fisher's r-to-Z transformation test for a correlation between IL-6 and volumetric measures. To achieve 80% power with a two-tailed Z test and 5% significance level, a correlation of |.23| can be detected for a sample of 150 subjects. Based on our preliminary data for IL-6 and for left CA2-3 we have a correlation of .33.

Aim 2: Characterize the effects of treatment on depression and the association with inflammation. Hypothesis 2a: Subjects randomized to treatment will have greater normalization of IL-6 and functional connectivity compared to those randomized initially to placebo. To achieve 80% power with a two-tailed t-test and 5% significance level, a mean difference of 2.1 can be detected with a standard deviation of 3.6 for a sample of 50 medicated and 50 nonmedicated subjects. Based on our preliminary data for IL-6, the mean (SD) difference, between the nonmedicated and medicated group for IL-6 is 2.7 (3.6). We will test Hypothesis 2a for improvement in functional connectivity with repeated measures ANOVA with the treatment group x time interaction result testing whether improvement in the outcome variables (increase in hippocampus and amygdala connectivity to DLPFC and AC) is greater in the treatment group than the placebo group, over and above non-specific changes over time (e.g., practice effects, naturalistic changes) that would be seen also in the control group. Our sample size of 100 with 50 in each group provides 80% power to detect a moderate effect size of .38 with .7 intraclass correlation on the group x time interaction, based on a two-tailed F-test with 5% significance level and assuming 10% attrition.

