### **3.3 *Suicidal Ideation and Behavior***

Plan for assessing suicidal ideation and behavior: The drug, escitalopram, will be administered to a portion of the participants in this study. Escitalopram does interact with the central nervous system as an antidepressant. Because it is an antidepressant, it is not expected to cause or contribute to the development of suicidal ideation or behavior. However, to monitor for a potential increase in risk of suicidal thinking and behavior, a safety protocol has been developed and plans are in place to evaluate all participants for clinical worsening and suicidality throughout participation in this study.

Safety Protocol to address potential risk of clinical worsening and suicidality:

As part of this study protocol, depressed patients will be enrolled and will be receiving anti-depressant medication, escitalopram. Current suicidality at the time of consent deems potential participants as ineligible to participate, thus suicidal patients will be screened out of the study. However, it is recognized the patients could possibly experience clinical worsening and potentially become suicidal. This possibility is unlikely for those who are receiving escitalopram since this medication is an anti-depressant and it is prescribed for the specific purpose of treating depressed mood.

To address the risk of suicidality, all patients will be closely monitored and they will receive psychiatric evaluations at baseline, weeks 1, 2, 4, and 6, as well as during all of these time points during the open label phase. The Montgomery-Asberg Depression Rating Scale will be administered at each follow-up visit to evaluate the presence of depressive symptoms.

Additionally, participants will be provided with phone numbers of research staff and they will be instructed to contact the staff if clinical worsening occurs. If research staff become aware of clinical worsening or suicidality, they will immediately intervene and activate safety procedures.

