### **5.3 Assessment measures and neuropsychiatric tests**

The following assessment measures and neuropsychiatric tests will be used:

Structured Clinical Interview for DSM-IV Axis I Disorders (SCID-I - Abbreviated version). The Structured Clinical Interview for DSM-IV Axis I Disorders (SCID-I) is a semi-structured interview for making Axis-I diagnoses according to the DSM-IV, and usually takes 60-90 minutes to administer. We will perform only the overview portion;

Montgomery-Asberg Depression Rating Scale (MADRS). The ten-item MADRS will be used to determine the presence of and severity of current depressive symptoms, and will be the primary outcome measure of depression severity in this study. The MADRS is included as it was used in our previous studies and will allow for comparison;

Hamilton Rating Scale for Depression (HAMD). All patients and controls will also be assessed using the HAMD, 17-item version, to determine the presence of any current depressive symptoms. The HAMD is included as it is more widely used in the US than the MADRS;

Montreal Cognitive Assessment (MOCA): This short test of visual and verbal functioning and delayed recall gives an indication of cognitive decline and dementia..

Framingham scale. For each subject we will rate a vascular risk factor (VRF) total score using the approach of the Framingham Study (Wolf et al., 1991), which gives a validated number based on the presence and severity of VRFs, weighted according to their predictive power for stroke;

Cumulative Illness Rating Scale-Geriatric (CIRS-G). A history of major illnesses and treatments will be taken, and the Cumulative Illness Rating Scale-Geriatric (CIRS-G) will be completed by the evaluating physician at the start of the trial (Miller et al., 1992). The CIRS-G covers all major systems (cardiovascular, pulmonary, renal, genitourinary, etc), and provides scores for current and past medical illnesses, including a global composite score that will be used as a measure of medical morbidity;

CONFIDENTIAL

The following Self-Report Questionnaires will be distributed:

Perceived Stress Scale (PSS). We will use the PSS score, a validated measure of subjective life stress to characterize the relationship between inflammatory cytokine levels, subjective stress, depression severity and treatment response. It is the most widely used measure of subjective stress;

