
## 6.2 Variables to be used in hypothesis testing

- 1) For measure of cytokine levels we will measure these in CSF and blood: Primary measure IL-6 pre- and post-treatment.
- 2) Hippocampus, including subvolume analyses and Amygdala volumes: Left and right volumes will be separately measured and standardized by cortical volumes before being entered in analyses. Prefrontal cortical thickness: L & R orbitofrontal, superior frontal and frontal pole.
- 3) Antidepressant treatment response determined using the MADRS score following antidepressant treatment covaried on baseline MADRS score.
- 4) Neuropsychological function as determined by factor scores from episodic memory and executive function.

CONFIDENTIAL

5) Resting state functional connectivity of the hippocampus and amygdala to anterior cingulate (AC) and dorsolateral prefrontal cortex (DLPFC).

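### The plan gives no role to the MADRS scores from weeks 1, 2 and 4, which leaves the celecoxib-versus-placebo contrast on MADRS open to avoidable dropout bias

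*Combined protocol and SAP*

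**What the plan says.** Section 6.1 outlines a repeated measures design with two time points and puts MADRS-type data inside it: "The data collected at two time points to be included in analysis (pre- and post-treatment) will be the depression severity". The estimation model is then described as "repeated measures ANOVA (analysis of variance) or mixed model repeated measures design", with no visits, covariance structure or randomized arm named. The only between-person factor given is case-control status.

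Sections 2.1 and 6.2 define the depression endpoint in the same two-point form: "Antidepressant treatment response determined using the MADRS score following antidepressant treatment covaried on baseline MADRS score". Section 5.3 says the MADRS "will be the primary outcome measure of depression severity in this study".

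More data are collected than this uses. Section 3.3 states: "The Montgomery-Asberg Depression Rating Scale will be administered at each follow-up visit to evaluate the presence of depressive symptoms". Section 2.2 puts the follow-up visits at weeks 1, 2 and 4, and the flow-chart in 12.1 has depression scales at baseline and weeks 1, 2, 4 and 6 for depressed participants in both arms.

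On missing data, 6.1 lists loss to follow-up as a source and says only: "We will employ multiple imputation". Section 2.7 has one arm calculation with a loss rate, for functional connectivity, "assuming 10% attrition".

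Hypothesis 2c in section 1.1 predicts a better depression score with celecoxib than with placebo. Section 6.3 contains no analysis for it.

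**The concern.** A participant who leaves after week 4 has four MADRS scores (baseline, weeks 1, 2 and 4). A two-point model, or imputation built on baseline alone, can use only one of them. That matters if leaving is related to the interim course, and the protocol makes it so: section 10.2 withdraws participants whose depressive symptoms worsen or who cannot tolerate escitalopram. Section 10.5.2 adds exclusion on blood pressure, which need not follow MADRS and could fall more on the celecoxib arm.

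If those who leave one arm are the ones doing badly, and those who leave the other are not, the participants left at week 6 are no longer comparable, even when the dropout rates are equal. Baseline MADRS is a weak predictor of where a leaver was heading; the last interim score is a much better one. At stake is a listed primary outcome and the randomized comparison on it.

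**Working it through.** **Nothing to reproduce.** The documents give no power or precision figure for MADRS. The only input they supply is the loss rate: 10%, with 50 per arm. Every SD, correlation and dropout rule below is an assumption.

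**Simulation in SD units.** Scores at weeks 0, 1, 2, 4 and 6; true week-6 effect −0.50 SD; correlation 0.90 or 0.85 per week of separation, so baseline to week 6 is 0.90^6 = 0.53 or 0.85^6 = 0.38; 100,000 per arm, 4 repeats. From week 2 on, the chance h of leaving before each visit follows logit(h) = a + b·x, where x is the last observed score, centred, in SD units.
- Same in both arms: a = −3.6, b = 1.
- Placebo only: placebo as above; celecoxib leavers random with a = −3.33, b = 0. Check: h = 1/(1 + e^3.33) = 0.0346, and over three visits 1 − (1 − 0.0346)³ = 0.10.
- Opposite: b = 1 on placebo, b = −1 on celecoxib, a = −3.6.

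Estimates at about 10% loss (10–13%), for weekly correlation 0.90 / 0.85:

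| Mechanism | No loss | Two-point, completers | Imputed from baseline only | Imputed by arm with weeks 1, 2, 4 | Two-point bias |
|---|---|---|---|---|---|
| Same in both arms | −0.501 / −0.494 | −0.496 / −0.487 | −0.496 / −0.487 | −0.501 / −0.494 | 0.005 / 0.007 |
| Placebo only | −0.498 / −0.497 | −0.468 / −0.464 | −0.466 / −0.464 | −0.497 / −0.497 | 0.030 / 0.033 |
| Opposite | −0.501 / −0.493 | −0.433 / −0.417 | −0.433 / −0.417 | −0.502 / −0.494 | 0.068 / 0.076 |

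At about 20% loss the two-point bias is 0.011 / 0.010, 0.060 / 0.066 and 0.128 / 0.143. Imputing from baseline alone does no better than completers. Adding the interim visits, which in large samples is equivalent to an all-visit mixed model, brings the bias to zero within 0.003.

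**Dropout on the unseen score.** Let x be the current, unrecorded score instead (missing not at random, MNAR). In the placebo-only case at 10% loss, the bias falls with interim data from 0.051 to 0.029 (43% removed) or from 0.060 to 0.036 (40%). At 20% it falls from 0.103 to 0.061 (41%) or from 0.117 to 0.076 (35%).

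**Simulation in MADRS points.** Assumed SD rising from 5 at baseline to 8.5 at week 6; correlation with week 6 rising from 0.35 at baseline to 0.80 at week 4; true effect −3.0. Intermediate correlations and leaving probabilities varied between runs.
- Placebo leavers are those above baseline, celecoxib leavers random, 9–13% loss: two-point ANCOVA gives −2.2 to −2.5. The shortfall of 0.5–0.8 points is 0.5/8.5 = 0.06 to 0.8/8.5 = 0.09 SD. At 13.5% loss it gives −2.1, a shortfall of 0.9/8.5 = 0.11 SD.
- Same rule in both arms, 10–15% loss: about −2.8 to −2.9, a shrinkage of up to roughly 6–8%, or about 0.2 points.
- Using all visits: about −3.0 in both cases.

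**Against sampling error.** With 50 × 0.9 = 45 per arm, the SE of the arm difference is about 8.5·√(1 − 0.35²)·√(2/45) = 1.7 points. The shared-mechanism bias is about 0.2/1.7 = 0.1 SE; the arm-different bias of 0.5–0.8 points is about 0.3–0.5 SE.

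**Precision.** If dropout is random, the all-visit SE is 2.5% smaller at 10% loss and 4% smaller at 20%. If only worseners leave, it can be 2–3% larger.

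**The case against.** A reader might infer that the plan discards the interim scores. The documents do not say that. Section 6.1 commits to multiple imputation without naming its variables, presents the two-point description as a basic outline, and allows a mixed model. The interim MADRS could enter either. This stands as far as it goes: the defect is that no role is assigned. But a mixed model fitted to two time points uses no interim data, and an unspecified imputation model is no assurance.

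A reader might also infer that the week-6 contrast will be materially biased. That is not shown. The symptom rule in 10.2 is the same for both arms, both arms take escitalopram, and under section 4.6 all but one team member are blind. For a shared mechanism the bias is close to zero. The larger figures need a mechanism that differs by arm, which the documents make plausible through side-effect and blood-pressure withdrawals but do not state.

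Nor can one say that the interim data would remove the bias outright. They do so only if dropout depends on observed MADRS (missing at random, MAR). Withdrawals for tolerability or blood pressure need not follow MADRS at all.

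Finally, interim MADRS cannot help impute the 50 controls' outcomes: section 2.2 says controls do not attend weeks 1, 2 and 4.

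**Conclusion.** The point holds as an avoidable risk to a listed primary outcome. Sections 6.1 and 6.2 set a two-point analysis of MADRS, no stated analysis uses weeks 1, 2 and 4, and section 10.2 ties withdrawal to the interim course. The arm contrast in hypothesis 2c, which lacks an analysis of its own in 6.3, is where the bias would fall, and it would act towards no effect in the scenarios examined.

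At about 10–15% loss the size is about 0.01 SD (up to roughly 6–8% of a 3-point effect under the other assumptions) if both arms share the dropout mechanism, and about 0.03–0.1 SD if they do not. Using all visits removes it under MAR and about one third to one half of it otherwise. The amounts depend on assumed SDs, correlations and dropout rules. What holds across the scenarios is that the two-point analysis was never the less biased one. This should be changed; it is not fatal to the trial.

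**What to change.** In 6.1 and 6.3:

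- For depressed participants, analyse MADRS at weeks 1, 2, 4 and 6 with a mixed model for repeated measures (baseline MADRS, arm, visit, arm × visit, unstructured covariance). Name the week-6 celecoxib-minus-placebo difference as the MADRS result for hypothesis 2c.
- State that the multiple imputation of depressed participants' other week-6 outcomes is done by arm and includes MADRS at weeks 1, 2 and 4. Exclude controls from this part, since they lack those visits.
- Add a simple MNAR sensitivity analysis, for example shifting imputed week-6 MADRS in leavers by a pre-stated range of amounts, separately by arm.
- Keep the two-point model for measures taken only twice.

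The cost is SAP wording and slightly more programming, with no new visits, data or participants. The SE may be a few percent larger if only worseners leave, and a few percent smaller if dropout is random.
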